6.1.2 Analysis Populations

Full Analysis Set (FAS) will be composed of all randomised patients (according to ITT principle, i.e. analysed based on the initial treatment assignment), having used at least one dose of investigation medication and for whom at least one post-baseline performance evaluation will be available.

Per protocol set (PP) will be a subset of the FAS without major protocol deviation. The precise reasons for excluding patients from the PP set will be defined and documented before breaking the blind during the BR meeting.

Safety population (SAF) will be composed of all patients exposed to the investigation Medical Device, i.e. having used at least one administration of the investigational Medical Device.

Note: Enrolled patients will be patients who have signed the informed consent and for whom the screening visit has been recorded in the e-CRF.

The **Eligible Eye** will be defined by following conditions:

- Oxford 0-15 score ≥ 4 and ≤ 9 AND;
- At least one of the following objective signs:
 - o Schirmer test ≥ 3 mm/5 min and ≤ 9 mm/5 min, **Or**
 - o Sum of 3 TBUT measurements ≤ 30 seconds.
 - o **And** without ophthalmological exclusion criterion

For patient with one eligible eye, this eye is considered as the “Worst eye” (study eye for primary analysis).

For patients with both eligible eyes or no eligible eye, the **Worst Eye** will be:

- Eye with the worst Oxford score;
- If same Oxford score in both eyes: eye with the worst Schirmer score;
- If same Oxford and Schirmer scores in both eyes: eye with the worst TBUT score;
- If same Oxford, Schirmer and TBUT scores in both eyes: right eye.

Note: worse Oxford score means highest value, whereas worse Schirmer score or worse TBUT score means lowest value.

The opposite to the worst eye is the **Contralateral Eye**.

Eligible eyes and Worst eye will be validated during the BR.

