6.2 Disposition of Patients

Descriptive statistics will be provided. No statistical test will be performed.

- Study dates: first date and last date will be provided for selection visit, inclusion visit and last visit (visit 5 or early withdrawal).
- Number and percentage of patients in each country and each site will be provided in FAS and Safety set.
- Status of patients:
 - Among all patients: number and percentage of patients selected and not selected, reason if not selected (as reported by the investigator at the selection visit)
 - Among selected patients: number and percentage of patients who attended inclusion visit, number and percentage of patients included and not included, reason if not included (as reported by the investigator on end-of-study page: Adverse event, lack of performance, withdrawal by subject, lost to follow-up, screen failure, other)
 - Among included patients: randomised (Yes, No)
 - Among randomised patients: number and percentage of patients with visits done (for each visit: Yes, No), visit type if Visit 5 done (Day 84 +/-7 days, Premature discontinuation visit), has the patient completed the study (Yes, No), reason if study not completed (Adverse event, lack of performance, withdrawal by subject, lost to follow-up, screen failure, other)

Non-selected patients, non-included patients and early withdrawals will be individually listed.

Note: In case of withdrawal, withdrawal visit will be re-assigned depending to the date of withdrawal. The withdrawal visit will be re-assigned to the closest planned missing visit (D8, D35 or D84). All re-assigned withdrawal visits will be discussed during BR and recorded in the BR meeting minutes.

- Analysis sets:
 - From randomised patients: Number and percentage in safety population, number and percentage of patients excluded from safety population and reason(s) for exclusion
 - From safety population: Number and percentage in FAS, number and percentage of patients excluded from FAS and reason(s) for exclusion
 - From FAS: Number and percentage in PP, number and percentage of patients excluded from PP and reason(s) for exclusion
 - Number and percentage of patients with major and minor protocol deviations, globally and for each section of deviation (inclusion criteria deviation, exclusion criteria deviation, randomisation, visit windows and chronology, run-in treatment compliance, IMD compliance, primary performance endpoint and secondary efficacy endpoints, other), in FAS.

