6.4 Subgroup analysis

Patients will be classified without or with possible impact of COVID-19 pandemic based on their Selection visit date respectively up to and including 18-MARS-2020, or after the 18-MAR-2020. The following summaries will be performed:

- o Number (%) of patients in each analysis set and reasons for exclusion by possible impact of COVID19
- o Number (%) of patients in each country by possible impact of COVID-19
- o Number (%) of premature withdrawal by possible impact of COVID-19
- o Protocol deviations by possible impact of COVID-19
- o Demographic characteristics by possible impact of COVID-19

Analysis sets will be presented on all randomised subjects, protocol deviation on FAS population, whereas countries, premature withdrawal and demographic characteristics will be presented on FAS and SAF populations.

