8 TABLES, LISTING AND FIGURES

8.1 Planned tables

Part 6.1 and 6.2: Disposition of patients

Table 1.1: First date and last date of selection visit, inclusion visit and last visit – All screened patients

Table 1.2: Number (%) of patients selected/not selected and reasons in case of non-selection – All screened patients

Table 1.3: Number (%) of patients who attended inclusion visit, number of patients included/not included and reasons in case of non-inclusion – Selected patients

Table 1.4: Number (%) of patients randomised/not randomised and reasons in case of non-randomisation – Included patients

Table 1.5: Number (%) of patients at each visit and type of last visit – Randomised patients

Table 1.6a: Number (%) of patients who completed the study and reasons in case of withdrawal – Randomised patients

Table 1.6b: Number (%) of patients who completed the study and reasons in case of withdrawal by possible impact of COVID-19 – SAF population

Table 1.6c: Number (%) of patients who completed the study and reasons in case of withdrawal by possible impact of COVID-19 – FAS population

Table 1.7a: Number (%) of patients in each population and reasons of exclusion – Randomised patients

Table 1.7b: Number (%) of patients in each population and reasons of exclusion by possible impact of COVID-19 – Randomised patients

Table 1.8a: Number (%) of patients in each country and site – FAS population

Table 1.8b: Number (%) of patients in each country and site by possible impact of COVID-19 – FAS population

Table 1.8c: Number (%) of patients in each country and site – SAF population

Table 1.8d: Number (%) of patients in each country and site by possible impact of COVID-19 – SAF population

Table 1.9: Time since inclusion for each visit – FAS population

Table 1.10: Study duration – FAS population

Table 1.11a: Protocol deviations – FAS population

Table 1.11b: Protocol deviations by possible impact of COVID-19 – FAS patient

Part 6.3: Demographic and baseline characteristics

Table 2.1a: Demographic characteristics – PP population
Table 2.1b: Demographic characteristics – FAS population
Table 2.1c: Demographic characteristics by possible impact of COVID-19 – SAF population
Table 2.1d: Demographic characteristics by possible impact of COVID-19 – FAS population
Table 2.2a: History of Dry Eye– PP population
Table 2.2b: History of Dry Eye– FAS population
Table 2.3a: Ocular medical history other than the studied disease by SOC and PT – PP population

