8.2 Planned listings

Listings 3 and 4 will include PP and FAS populations (as variable) and listing 5 will include FAS population.

Part 6.2:

Listing 1: Non-selected patients, non-included patients and early withdrawals – All screened patients
Listing 2: Protocol deviations – FAS population

Part 6.3:

Listing 3: Other aetiology of Dry Eye – Safety population

Part 6.5:

Listing 4: Previous and concomitant treatments – Safety population

Part 6.6:

Listing 5: Daily dose regimen different from 2 to 4 instillations/day – Safety population

Part 6.7:

Listing 6: OSI score – FAS population

Part 6.8:

- Listing 7: Listing of individual data of overall systemic TEAEs – Safety population
- Listing 8: Listing of individual data of overall ocular TEAEs – Safety population
- Listing 9: Listing of individual data of overall systemic SAEs – Safety population
- Listing 10: Listing of individual data of overall ocular SAEs – Safety population
- Listing 11: Listing of individual data of overall systemic SADEs – Safety population
- Listing 12: Listing of individual data of overall ocular SADEs – Safety population
- Listing 13: Listing of individual data of non-emergent systemic AEs – Enrolled population
- Listing 14: Listing of individual data of non-emergent ocular AEs – Enrolled population
- Listing 15: Listing of COVID-19 AEs – Enrolled population

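### Withdrawals by COVID-19 period are tabulated only in the SAF and FAS, so randomised patients lost without any visit can drop out of the only by-period withdrawal tables

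*SAP*

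**What the plan says.** SAP 6.2 reports completion and the reasons for not completing among randomised patients. The planned table follows that: "Table 1.6a: Number (%) of patients who completed the study and reasons in case of withdrawal – Randomised patients".

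For the split by COVID-19 period, SAP 6.4 keeps the analysis-set counts on all randomised patients but moves withdrawal to narrower sets: "whereas countries, premature withdrawal and demographic characteristics will be presented on FAS and SAF populations". SAP 8.1 implements this with "Table 1.6b: Number (%) of patients who completed the study and reasons in case of withdrawal by possible impact of COVID-19 – SAF population" and "Table 1.6c: Number (%) of patients who completed the study and reasons in case of withdrawal by possible impact of COVID-19 – FAS population". No reason is given for the change of base.

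The sets are defined as follows.

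- FAS (SAP 6.1.2): randomised, dosed, and "for whom at least one post-baseline performance evaluation will be available".
- SAF (SAP 6.1.2): one administration of the device is enough. No return visit is required.
- SAF as derived (SAP 3.3): the flag SS is set to 1 only if a treated eye is recorded at Day 35 or Day 84, and to 0 otherwise. The FAS flag in the same section requires SS to be 1.

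The period variable (SAP 3.3 and 4.3) depends on screening date, up to and including 18 March 2020 or later. SAP 4.3 gives its purpose as examining recruitment bias around the pause in enrolment.

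**The concern.** A table of withdrawals should count everyone who could have withdrawn. The FAS condition depends on the outcome being tabulated: a randomised patient who is never seen again is a withdrawal, yet leaves both the numerator and the denominator. The same happens in the SAF if membership is programmed from the Day 35 and Day 84 records.

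The direction of the error is known. Each omitted patient is a non-completer, so the by-period withdrawal percentage can only come out too low. If such losses are spread unequally over the two periods, the comparison between periods is distorted as well. This matters because SAP 5.1 says that missing data exceeded the plan, partly because of the pandemic. A reader will look to these tables to see how far losses differ between the periods.

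**Working it through.** **1. Who is counted where.** Following three kinds of randomised non-completer through the definitions:

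| Patient | Table 1.6a (randomised) | Table 1.6b, SAF by SAP 6.1.2 | Table 1.6b, SAF by SAP 3.3 | Table 1.6c (FAS) |
|---|---|---|---|---|
| Withdraws; withdrawal visit done, with a treated-eye record and an evaluation | in | in | in | in |
| Used the device, no later visit of any kind | in | in | out, unless a treated eye is recorded for Day 35 or Day 84 | out |
| Never used the device, no later visit | in | out | out | out |

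Only Table 1.6a holds all three, and it is not split by period.

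**2. Whether another table fills the gap.** "Table 1.7b: Number (%) of patients in each population and reasons of exclusion by possible impact of COVID-19 – Randomised patients" is split by period and uses the randomised base. Its reasons, however, are reasons for exclusion from an analysis set, not completion status or reason for withdrawal. "Listing 1: Non-selected patients, non-included patients and early withdrawals – All screened patients" gives individual records, not a summary. No planned table combines withdrawal, its reason, the period and the randomised base.

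**3. The plan's own attrition figure.** From SAP 5.1, 76 evaluable patients at 15% non-evaluable need 76 / (1 − 0.15) = 89.4, rounded up to the stated 90. The reported 101 randomised for about 76 evaluable implies 1 − 76/101 = 24.8% non-evaluable. These figures concern PP evaluability. They do not give the number of withdrawals or the number outside the SAF or FAS.

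**4. Size under assumptions.** Let R be the number randomised, W the number of withdrawals, and k the number of those who fall outside the tabulated set.

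- Randomised base: W / R
- Restricted base: (W − k) / (R − k)
- Shortfall: k(R − W) / [R(R − k)]

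R = 101 comes from SAP 5.1. W and k are assumed.

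| W | Randomised base | k = 1 | k = 3 | k = 5 |
|---|---|---|---|---|
| 10 | 10/101 = 9.9% | 9/100 = 9.0% | 7/98 = 7.1% | 5/96 = 5.2% |
| 15 | 15/101 = 14.9% | 14/100 = 14.0% | 12/98 = 12.2% | 10/96 = 10.4% |
| 25 | 25/101 = 24.8% | 24/100 = 24.0% | 22/98 = 22.4% | 20/96 = 20.8% |

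From the shortfall formula, before rounding:

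- k = 1: from 1 × 76 / (101 × 100) = 0.8 points (W = 25) to 1 × 91 / (101 × 100) = 0.9 points (W = 10).
- k = 3: from 3 × 76 / (101 × 98) = 2.3 to 3 × 91 / (101 × 98) = 2.8 points.
- k = 5: from 5 × 76 / (101 × 96) = 3.9 to 5 × 91 / (101 × 96) = 4.7 points.
- k = 0: no difference.

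The documents do not give the numbers by period, so this uses the whole trial. Within one period R is smaller, and for the same underlying rate a given k has a larger effect.

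**The case against.** The best reply is that little is lost. Protocol 6.7.3 has the final-visit investigations done for patients who discontinue. SAP 4.3 reassigns those data to a planned visit and uses them. The FAS flag accepts any one of a long list of assessments at any post-baseline visit. Only patients with no visit at all, not even a withdrawal visit, are certain to fall outside the FAS. All of this stands, and it limits the point to that group.

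A reader might go further in several ways that the documents do not support.

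- *That both sets, by definition, exclude patients who never returned.* SAP 6.1.2 keeps any dosed patient in the SAF. The exclusion from Table 1.6b arises under the SAP 3.3 derivation, which conflicts with that definition, or when the patient never used the device.
- *That early losses disappear from the report.* Table 1.5 shows attendance and Table 1.6a shows withdrawals on all randomised patients. Table 1.7b counts exclusions by period, and Listing 1 gives the individual cases. What is missing is one cross-tabulation.
- *That the losses sit in the later period.* The split is by screening date. A patient screened on or before 18 March 2020 whose follow-up fell during the interruption is coded as not affected.
- *That retention in the PP set is flattered by taking its percentage from the FAS.* SAP 6.2 labels that base openly ("From FAS: Number and percentage in PP, number and percentage of patients excluded from PP and reason(s) for exclusion"). The table shell shows each nested count and the randomised total. SAP 5.1 itself states 101 randomised for about 76 evaluable.

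**Conclusion.** The point holds as a gap in descriptive reporting. The by-period summary of completion and withdrawal reasons is restricted to the SAF and FAS, while the same summary without the split uses all randomised patients. Randomised patients lost without any post-baseline or withdrawal visit are absent from Table 1.6c. They are also absent from Table 1.6b if the SAF is built from the SAP 3.3 flag. The by-period percentage is too low whenever such patients exist.

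The size is unknown and may be zero. The range of 0.8 to 4.7 points rests on assumed values of 1 to 5 omitted patients and 10 to 25 withdrawals out of 101.

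It would be wrong to infer any effect on the non-inferiority result. These tables feed no model, and the primary estimate, its confidence interval and the decision rule are unchanged.

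**What to change.** In SAP 6.4 and 8.1, produce the completion and withdrawal-reason table by COVID-19 period on all randomised patients, by arm, as a by-period version of Table 1.6a. Presentation by arm already follows from the general rule for disposition in SAP 5.2. Tables 1.6b and 1.6c can be kept, at most, as supportive.

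Reconcile the SS derivation in SAP 3.3 with the SAF definition in SAP 6.1.2, so that one rule decides whether a dosed patient without a Day 35 or Day 84 treatment record is in the SAF. The FAS flag requires SS, so this affects both sets.

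The table itself costs one more output or a changed filter on data already collected. Reported by-period withdrawal rates may come out slightly higher.

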8.2 Planned listings

Listings 3 and 4 will include PP and FAS populations (as variable) and listing 5 will include FAS population.

Part 6.2:

Listing 1: Non-selected patients, non-included patients and early withdrawals – All screened patients
Listing 2: Protocol deviations – FAS population

Part 6.3:

Listing 3: Other aetiology of Dry Eye – Safety population

Part 6.5:

Listing 4: Previous and concomitant treatments – Safety population

Part 6.6:

Listing 5: Daily dose regimen different from 2 to 4 instillations/day – Safety population

Part 6.7:

Listing 6: OSI score – FAS population

Part 6.8:

- Listing 7: Listing of individual data of overall systemic TEAEs – Safety population
- Listing 8: Listing of individual data of overall ocular TEAEs – Safety population
- Listing 9: Listing of individual data of overall systemic SAEs – Safety population
- Listing 10: Listing of individual data of overall ocular SAEs – Safety population
- Listing 11: Listing of individual data of overall systemic SADEs – Safety population
- Listing 12: Listing of individual data of overall ocular SADEs – Safety population
- Listing 13: Listing of individual data of non-emergent systemic AEs – Enrolled population
- Listing 14: Listing of individual data of non-emergent ocular AEs – Enrolled population
- Listing 15: Listing of COVID-19 AEs – Enrolled population

8.3 Planned figures

Figure 1: Flowchart

9 REFERENCES

NA.

10 APPENDICES

10.1 Appendix 1: Level of validation for analyses programming

This chapter documents the validation of the statistical analysis programs. The level of validation is defined with reference to the procedure “Programming of the statistical analysis”. All the analyses and programs have a default validation level “Basic + NC”. Analysis below have a CR validation level:

Analyses	Validation level	Programs
Randomisation (when unblinding)	CR	FICH
Populations	CR	FICH
Derived data	CR	FICH
Primary efficacy endpoint (section 7.6.1)	CR	ANA_PRINC
Ocular unusual sensation UPON INSTILLATION	CR	ANA_SAFE
Adverse events	CR	ANA_SAFE

Key:

Basic = Corresponds to the self-check of the programming by any person who is required to program, as well as the checking of derived variables (see self-check frame)

NC (non-critical) = The tables, listings and figures compiled in a single document shall be verified by one qualified person other than the program developer with the support of the CRF and SAP for the study.

CR (critical) = A double programming and a comparison of the results should be performed by one qualified person other than the program developer.
